8.3 Recruitment..... 20

8.4 Written Informed Consent 21

8.5 Process of Consent..... 21

8.6 Certificate of Confidentiality..... 22

9. REFERENCES..... 22

10. APPENDICES AND RDCRN INFORMED CONSENT TEMPLATES 23

10.1 Appendix 23

10.2 Informed Consent for Healthy Volunteers 25

10.3 Informed Consent for Urea Cycle Disorder Participants 40

1. Protocol Synopsis

Interventional Synopsis

Protocol Number:	5115
Protocol Title:	Manipulating the Gut Microbiome in Urea Cycle Disorders
Study Chair:	[name] [name]
Study Co-Chair:	[name]
Statistician:	[name]
Consortium:	Urea Cycle Disorders Consortium
Participating Sites:	Children's National Medical Center
Activation Date:	Pending
Current Status:	Pre-enrollment
Sample Size:	Group 1: 8 healthy adult subjects Group 2: 8 adult subjects with urea cycle disorders
Target Enrollment Period:	Group 1: 1 year Group 2: 2 years
Study Phase	I/II
Study Design:	Open-label, cross-over
Primary Study Objective:	The objective is to determine if acetohydroxamic acid (AHA) can prevent hydrolysis of urea by inhibiting the bacterial urease of gut flora of both healthy control adults as well as adults with urea cycle disorders
Secondary Study Objective(s):	Determine if the proposed dose of acetohydroxamic acid is safe
Study Population and Main Eligibility/ Exclusion Criteria:	
A subject may be included in the study if all of the following criteria are met:
 
For Group 1 (healthy adults):
 
 - Ages 18-60 years - Compliant with receiving medications orally and intravenously - Compliant with providing blood and urine samples 
For Group 2 (adult UCD patients):
 
 - Ages 18-60 years - Compliant with receiving medications orally and intravenously - Compliant with providing blood and urine samples - Established diagnosis of CPSD, OTCD, ASSD or ASLD as follows: 
 o Diagnosis of CPS I deficiency, defined as decreased (less than 20 % of control) CPS I enzyme activity in liver or an identified pathogenic mutation o Diagnosis of OTC deficiency, defined as the identification of a pathogenic mutation, linkage analysis in an affected family, less than 20% of control of OTC activity in the liver, or elevated urinary orotate (greater than 20 uM/mM) in a random sample or following allopurinol loading with absence of argininosuccinic acid o Diagnosis of AS deficiency (Citrullinemia), defined as a greater than or equal to 10-fold elevation of citrulline in plasma, decreased AS enzyme activity in cultured skin fibroblasts or other appropriate tissue, or identification of a pathogenic mutation in the AS gene o Diagnosis of AL deficiency (Argininosuccinic Aciduria,

	
ASA), defined as the presence of argininosuccinic acid in the blood or urine, decreased AL enzyme activity in cultured skin fibroblasts or other appropriate tissue, or identification of a pathogenic mutation in the AL gene
 
A subject may not be included in the study if any one of the following criteria is met:
 
For both Group 1 and Group 2:
 
 - Current or prior Helicobacter pylori infection - Chronic gastrointestinal illness (e.g., inflammatory bowel disease) - Chronic renal failure - Taking probiotic medications within a week of study start date - Currently pregnant or lactating. Documentation of a negative pregnancy test within a week prior to testing is required, unless pre-menarchal or menopausal, experiencing menses that week, or other circumstances which preclude pregnancy (e.g. hysterectomy). - Presence of acute infection at the time of inclusion - Participation in any other clinical interventional trial or received experimental medication within the last 30 days - Any clinical or laboratory abnormality or medical condition that, at the discretion of the investigator, may put the subject at an additional risk by participating in this study
Treatment	
Agent-	Acetohydroxamic Acid (AHA, Lithostat)
Dosage, schedule, route of administration-	Single dose, 60 mg/kg PO
Safety Issues-	Bone marrow depression (leukopenia, anemia, and thrombocytopenia) has occurred in experimental animals receiving large doses of AHA. However, only a single dose will be administered in this study, and is not likely to result in this adverse effect.
Primary Outcome Measures:	Difference in the time-averaged level of blood $^{13}\text{CO}_2$ after a single bolus of intravenous [^{13}C]-Urea, measured on two occasions: once at baseline, and once 2-hr after an oral bolus of AHA
Secondary Outcome Measures:	Differences in blood [^{13}C]-Urea, Urea, Ammonia, Glutamine
Safety Variables	Hemoglobin, White blood count, platelets, AST, ALT, Bilirubin, Creatinine
Statistical Considerations (sample size and analysis plan):	Longitudinal linear regression models will assess and compare time averaged mean changes in blood $^{13}\text{CO}_2$, and blood levels of [^{13}C]-urea, ammonia and glutamine. A sample size of 8 crossover participants provides 90% power to detect a 20% relative difference in the time-averaged level of $^{13}\text{CO}_2$ in treatment with AHA versus non-AHA under a 2-tailed type I error of 0.05.
Sponsors (federal, state, foundation and industry support):	Rare Disorders Clinical Research Network, National Institutes of Health, National Institute of Child and Human Development Mission Pharmacal

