1.1 Overview

This project will study the efficacy and safety of the pharmacologic blockade of urease in the nitrogen salvage pathway of intestinal microbes in subjects with partial urea cycle disorders. Additional trapping of ammonia as excretable urea may result in improved nitrogen excretion and reduced ammonia levels.

Urea cycle disorders (UCDs) are a group of disorders resulting from a complete or partial deficiency of one of the 6 enzymes or 2 transporters that comprise the urea cycle, the essential biochemical pathway which converts toxic ammonia into urea. These disorders have as a common feature, a reduced or complete inability to convert ammonia into urea, thereby resulting in high ammonia levels, or hyperammonemia. If untreated, hyperammonemia may result acutely in lethargy and coma, and chronically in intellectual disability. Current treatment for hyperammonemia is suboptimal, thus the search for new treatments is critical.

The urease inhibitor, acetohydroxamic acid (AHA, Lithostat®, Mission Pharmacal), is an FDA-approved product for another indication- the treatment of struvite nephrolithiasis in chronic urinary tract infections in both adults and children^{1,2}.

It is known that many urea-splitting bacteria also exist in the gut, and that in healthy individuals, approximately 15-30% of blood urea is degraded via gut bacteria into ammonia³, which returns to the liver via the portal vein, only to be recycled into urea. This percentage of degraded urea may even be greater in patients with urea cycle disorders, who are on a low protein-diet⁴ and whose gastrointestinal contents thus likely have lower nitrogen content, promoting bacterial recycling of nitrogen from available urea. Additionally, urea hydrolysis has been shown to be greatest in infants⁵, precisely the age at which hyperammonemic episodes are the most frequent in UCD patients.

We intend to study if AHA can inhibit gut bacteria degradation of urea, thereby reducing the quantity of ammonia returning to the liver. We intend to investigate this by studying subjects on two occasions at least 3 days apart:

On the first occasion, subjects will receive an intravenous dose of ¹³C-urea. Following the intravenous bolus of ¹³C-urea, over the subsequent 4 hours, we will collect several sequential measurements of blood and urine biomarkers from an IV catheter placed in the other arm. The intent is to obtain baseline ¹³CO₂ kinetics in the subject.

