Enteral AHA has previously been administered to patients with hyperammonemia due to hepatic encephalopathy in two published reports^{6,7}. A single dose of oral 750 mg in adult patients was insufficient to result in any change in ammonia after 90 minutes in cirrhotic subjects free of *H. Pylori*⁷. However, in encephalopathy cirrhotic subjects administered AHA 20-60 mg/kg via naso-gastric tube, a statistically significant decreased in blood ammonia was observed⁶, with the effect most striking in subjects receiving a dose of 40-60 mg/kg/d.

This proposal would introduce a novel therapeutic approach for patients with UCD using a low-toxicity compound that may be particularly effective in patients with partial UCDs. There are two potential ways this approach may lower blood ammonia or excess nitrogen. The first is through blockage of new ammonia formation from urease. The second path may be increased consumption of residual dietary nitrogen by the gut flora in the absence of available nitrogen released through urease. Both effects may decrease the amount of nitrogen entering the portal vein. This new therapy will not interfere with other therapies, but would be complementary to them and may potentiate the nitrogen trapping effects of arginine and citrulline by preventing the degradation of the urea produced by their administration.

4. Study Design and Methods

This pilot crossover study will first evaluate the impact of AHA versus non-AHA primarily on ¹³CO₂ and secondarily on other biomarkers in healthy adults before applying the same crossover design to UCD subjects. A randomization table will determine if AHA or non-AHA will be performed first.

The figure below illustrates our study design:

Subjects will be required to fast for a minimum of 4 hours prior to beginning the study. Food consumption will not be permitted during the study; however subjects will be allowed to drink water or pedialyte throughout the study. Subjects will be observed and

various biomarkers will be collected throughout the 4-6 hours that they are studied. 5 mL of blood will be collected at each of the 7 time points shown above. Administration of [¹³C]-urea will be completed through an intravenous catheter. Blood draws will be done through the placement of a Heplock intravenous catheter on the opposite arm from where [¹³C]-urea was first administered. If there is not adequate vascular access, subjects will have a PICC (peripherally inserted central catheter) line placed instead.

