Recruitment and enrollment: See Section 4.3, 8.4-5

Follow-up: Subjects will be followed throughout the duration of their participation.

Data collection: See Sections 5.9, 6, 7

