4.4 Retention strategies

As the study involves only 2 days of participation, we anticipate retention to be near 100%.

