4.6 Schedule of Events

Subjects will be studied twice: once without and once with a single dose of acetohydroxamic acid, with the two study days at least 3-days apart.

Table 1. Laboratory investigations (each study day)

	Time point (min)							
	Baseline	0	30	60	90	120	180	240
Blood [¹³ C]-urea		X	X	X	X	X	X	X
Blood urea		X	X	X	X	X	X	X
Plasma glutamine		X	X	X	X	X	X	X
Ammonia		X	X	X	X	X	X	X
Blood ¹³ CO ₂		X	X	X	X	X	X	X
Urine [¹³ C]-urea		X						X
Urine urea		X						X
Safety labs:								
Hemoglobin	X							X
White blood count	X							X
Platelets	X							X
AST	X							X
ALT	X							X
Bilirubin	X							X
Creatinine	X							X

'Baseline' indicates at a time 0 on days when AHA is not administered or at a time prior to AHA administration on the days where AHA is administered. In addition, some of the blood and urine samples will be saved at the Clinical and Translational Science Institute at CNMC for up to 3 years after the conclusion of the study to test for the metabolism of AHA, after which the samples will be discarded.

5. Safety Monitoring

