5.3 Expected/Known Risks/Discomforts/Adverse Events

A definition of expected adverse events associated with study intervention and procedures are outlined below.

Study Drug/Intervention:

AHA:

Acetohydroxamic acid has been an FDA approved medication for the treatment of struvite nephrolithiasis for over 25 years. According to the prescribing information, about 150 patients, including children, have been treated, most for periods of more than 1 year.

Well controlled, long-term animal studies that identify the carcinogenic potential of AHA treatment have not been conducted. Acetamide, a metabolite of AHA, has been shown to cause hepatocellular carcinoma in rats at oral doses 1,500 times the human dose. AHA is cytotoxic and was positive for mutagenicity in the Ames test.

The pharmacokinetics of AHA in man are well known: 36-65% of the oral dose of AHA is excreted unchanged in the urine. The plasma half-life of AHA is approximately 5-10 hours in subjects with normal renal function.

According to the AHA (Lithostat) prescribing information, adverse reactions have occurred in up to thirty percent (30%) of the patients receiving AHA. In some instances, the reactions were symptomatic: in others, only changes in laboratory parameters were noted. Adverse reactions seem to be more prevalent in patients with pre-existing thrombophlebitis and/or in patients with advanced degrees of renal insufficiency.

The following reactions have been reported:

- 30% - Mild headaches during the first 48 hours of treatment, responsive to standard therapy
- Tremulousness and nervousness
- 20% - Gastrointestinal symptoms (nausea, vomiting, anorexia)
- 15% - laboratory findings characteristic of a hemolytic anemia
- Non-pruritic, macular rash on the upper extremities and face, usually concomitantly with alcoholic beverages, with spontaneous resolution
- Superficial phlebitis

Acute toxicity has not occurred. Milder overdoses resulting in hemolysis have occurred in an occasional patient with reduced renal function after several weeks or months of continuous treatment.

There is a small risk that the blood ammonia level will rise during the study. This unlikely possibility, would mostly likely result from toxicity of the AHA to the liver.

13C Urea:

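### Safety of the dose is the secondary objective, but no adverse-event window is defined and scheduled observation can end 5–6 h after AHA, so headaches expected over 48 h can go unrecorded

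*Combined protocol and SAP*

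**What the plan says.** The synopsis lists as secondary objective: "Determine if the proposed dose of acetohydroxamic acid is safe". Section 6 gives no safety analysis and no criterion by which the dose would be judged safe.

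On follow-up, Section 4 says only: "Subjects will be followed throughout the duration of their participation". Section 4.4 gives the length of that participation: "As the study involves only 2 days of participation". On each day, according to Section 4, "various biomarkers will be collected throughout the 4-6 hours that they are studied". Section 1.1 says of the period after the tracer: "over the subsequent 4 hours, we will collect several sequential measurements of blood and urine biomarkers". Table 1 in Section 4.6 places the safety labs at Baseline and at 240 minutes, and the study days at least 3 days apart.

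Two design features that determine the length of follow-up are stated in conflicting ways:

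- **Order.** Section 4 and Appendix 10.1 randomise whether AHA comes first or second. Section 1.1 puts AHA on the second occasion.
- **Lag from AHA to tracer.** Section 1.1 and Appendix 10.1 give about 60 minutes. The primary outcome in the synopsis gives 2 hours.

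Section 5.3, citing the prescribing information, lists for 30%: "Mild headaches during the first 48 hours of treatment". It also lists gastrointestinal symptoms (20%) and laboratory signs of haemolytic anaemia (15%), without an onset time for either.

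**The concern.** A safety objective needs a stated period over which events are looked for, and that period should be the same for everyone whose data are combined. Here the only scheduled observation after AHA is the remainder of that study day, plus whatever a later study day happens to supply. Someone who takes AHA on the second day can complete the schedule exactly and leave 5–6 hours after the dose, well inside the 48 hours the protocol gives for its commonest listed reaction.

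The recorded frequency would then depend partly on how long people were observed and, if order is randomised, on the sequence to which they were allocated. An absence of events could be read as evidence of safety when it partly reflects short ascertainment and a very small sample.

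**Working it through.** **1. Time from AHA to last scheduled observation.** Time = lag from AHA to tracer + 240 min.

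- No AHA: 240 min = 4 h.
- Lag 60 min: 60 + 240 = 300 min = 5 h.
- Lag 2 h: 120 + 240 = 360 min = 6 h.

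This reproduces the 4–6 hours stated in Section 4.

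**2. Share of the 48 hours covered on the AHA day.** 5/48 = 10.4%; 6/48 = 12.5%. With the 5–10 h half-life in Section 5.3 and simple decay 0.5^(t/half-life), ignoring absorption, 50–71% of the drug remains at 5 h and 44–66% at 6 h.

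**3. Difference by sequence.** With randomised order, AHA-first participants return after at least 3 × 24 = 72 h, when Baseline safety labs are already scheduled. AHA-second participants have nothing scheduled beyond 5–6 h. The ratio is 72/6 = 12 to 72/5 = 14.4. With AHA always second, there is no difference by sequence, but nobody is scheduled for observation beyond 5–6 h.

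**4. Possible loss of headaches.** Let p = 30% be the rate over 48 h (Section 5.3, applied to a single dose by assumption). Let f be the share of those headaches that start by 5 h. The documents do not give f, so a range is shown; 10.4% corresponds to uniform onset over 48 h. The table assumes that later headaches in AHA-second participants go unreported and that AHA-first participants recall everything at their return.

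- AHA-second participants show p × f.
- With a 4:4 split, the expected number seen is 4 × 0.30 + 4 × 0.30 × f, of 8 × 0.30 = 2.4.
- With all 8 taking AHA second, the chance of seeing none is (1 − 0.30 f)^8.

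| f | Rate shown, AHA second | Expected seen of 2.4, 4:4 split | Chance of none, all 8 AHA second |
|---|---|---|---|
| 10.4% | 3.1% | 1.32 | 78% |
| 25% | 7.5% | 1.5 | 54% |
| 50% | 15% | 1.8 | 27% |
| 75% | 22.5% | 2.1 | 13% |
| 100% | 30% | 2.4 | 5.8% |

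**5. What zero events would show, even with full ascertainment.** The exact upper limit for 0 events in n is 1 − α^(1/n).

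- n = 8, one-sided 95%: 1 − 0.05^(1/8) = 31.2%.
- n = 8, two-sided 95%: 1 − 0.025^(1/8) = 36.9%.
- Both groups pooled, n = 16: 17.1% and 20.6%.

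With 8 participants, both limits lie above the 30% headache rate that the protocol itself cites.

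**The case against.** The last blood draw is not the end of adverse-event recording. Section 5.0 has events collected after each completed study. The deadlines in Section 5.4 run from when the site learns of an event, and Section 5.5 covers events that participants report. A headache mentioned by a participant after discharge can be recorded. This stands, and it rules out the inference that later reactions will necessarily be missed. It does not supply active ascertainment: none of these sections sets a window or a contact. The final visit and follow-up to resolution in Section 5.7 are written for participants who discontinue.

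Only headache carries the 48-hour figure. A reader might extend the point to haemolytic findings, but Section 5.3 gives no onset time for them, and the timing it does give for haemolysis relates to overdose during prolonged treatment in patients with reduced renal function. That extension is not supported. Headache is also described there as mild and treatable, which limits the clinical weight of missing some.

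The 30% comes from patients mostly treated for more than a year, on repeated daily dosing. After a single dose, onset may be concentrated in the first hours, so uniform onset may be near the pessimistic end. This stands; the 3% row is one assumption among several and not an estimate.

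The consent forms and the design figure are not in the supplied text, and Section 7.6 refers to a Manual of Procedures that is not supplied either. Any of these might describe later contact.

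Finally, no small pilot can demonstrate safety. True, and this is a reason to word the objective accordingly.

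**Conclusion.** The point holds in limited form. The supplied text defines no adverse-event window after AHA. Scheduled observation can end 5–6 h after the dose when AHA is given second, against at least 72 h when it is given first, and ends at 5–6 h for everyone if AHA is always second. Headaches that the protocol places in the first 48 hours can therefore go unrecorded.

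The size is uncertain. AHA-second participants might show anything from about 3% to 22.5% in place of an assumed 30%, as the share starting by 5 h runs from 10% to 75%. This rests on three assumptions: the prescribing-information rate applies to a single dose, later events in these participants are not volunteered, and AHA-first participants report fully on return.

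Two stronger conclusions might be drawn and are not supported. One is that unequal follow-up by sequence is a settled fact; it exists only if order is randomised, which the documents state inconsistently. The other is that a clean safety result would open the trial to participants with urea cycle disorders; the condition in Section 6 is a signal of effect on labelled CO₂, and the monitoring board reviews adverse events every 6 months (Section 5.1).

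Independently of follow-up, 0 events in 8 is compatible with a true rate of up to 31% (one-sided 95%) or 37% (two-sided), so the objective as worded cannot be met.

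**What to change.** 1. Restate the secondary objective as describing adverse events and safety-lab changes over the observed window after a single dose, with exact confidence limits for event proportions, and add this analysis to Section 6.
2. Define one adverse-event ascertainment window after the AHA day, identical for both sequences and reconciled with the 48 hours in Section 5.3. A telephone or message query by existing staff is enough.
3. Report the already scheduled second-day Baseline labs of AHA-first participants descriptively as post-AHA follow-up, and state that AHA-second participants have no equivalent late labs. The query in item 2 does not remove that difference in laboratory follow-up.
4. Reconcile the passages on AHA order (Section 1.1 against Section 4 and Appendix 10.1) and on the AHA-to-tracer lag (synopsis against Section 1.1 and Appendix 10.1). If the consent forms or the Manual of Procedures already specify later contact, bring that into the protocol.

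With item 2, planned coverage of the 48 hours rises from 10.4–12.5% to 100% for participants whose AHA day is their last. The cost is one brief contact per participant, some redrafting and a less favourable safety statement. No visit or blood draw is added.

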1.1 Overview

This project will study the efficacy and safety of the pharmacologic blockade of urease in the nitrogen salvage pathway of intestinal microbes in subjects with partial urea cycle disorders. Additional trapping of ammonia as excretable urea may result in improved nitrogen excretion and reduced ammonia levels.

Urea cycle disorders (UCDs) are a group of disorders resulting from a complete or partial deficiency of one of the 6 enzymes or 2 transporters that comprise the urea cycle, the essential biochemical pathway which converts toxic ammonia into urea. These disorders have as a common feature, a reduced or complete inability to convert ammonia into urea, thereby resulting in high ammonia levels, or hyperammonemia. If untreated, hyperammonemia may result acutely in lethargy and coma, and chronically in intellectual disability. Current treatment for hyperammonemia is suboptimal, thus the search for new treatments is critical.

The urease inhibitor, acetohydroxamic acid (AHA, Lithostat®, Mission Pharmacal), is an FDA-approved product for another indication- the treatment of struvite nephrolithiasis in chronic urinary tract infections in both adults and children^{1,2}.

It is known that many urea-splitting bacteria also exist in the gut, and that in healthy individuals, approximately 15-30% of blood urea is degraded via gut bacteria into ammonia³, which returns to the liver via the portal vein, only to be recycled into urea. This percentage of degraded urea may even be greater in patients with urea cycle disorders, who are on a low protein-diet⁴ and whose gastrointestinal contents thus likely have lower nitrogen content, promoting bacterial recycling of nitrogen from available urea. Additionally, urea hydrolysis has been shown to be greatest in infants⁵, precisely the age at which hyperammonemic episodes are the most frequent in UCD patients.

We intend to study if AHA can inhibit gut bacteria degradation of urea, thereby reducing the quantity of ammonia returning to the liver. We intend to investigate this by studying subjects on two occasions at least 3 days apart:

On the first occasion, subjects will receive an intravenous dose of ¹³C-urea. Following the intravenous bolus of ¹³C-urea, over the subsequent 4 hours, we will collect several sequential measurements of blood and urine biomarkers from an IV catheter placed in the other arm. The intent is to obtain baseline ¹³CO₂ kinetics in the subject.

On the second occasion, subjects will first receive an oral dose of AHA approximately 1 hour prior to the intravenous ¹³C-urea dose. Similar sequential measurements of blood and urine biomarkers will be performed. The intent is to observe a reduction in ¹³CO₂ when AHA is administered.

We intend to initially study a cohort of unaffected adult subjects. If successful, we will study adults with partial urea cycle disorders.

This study will be conducted in the Clinical Research Center (CRC) of the Clinical and Translational Research Institute (CTSI) of Children's National Medical Center (CNMC).

2. Specific Aims (Hypothesis and Objectives)

The specific aim is to investigate whether a single oral dose of AHA can inhibit intestinal bacterial urease in healthy subjects as well as in patients with partial UCDs, and whether it is safe. We propose a study with two components: the first without AHA, and the second after a single dose of AHA, 60mg/kg/d. We will evaluate whether AHA will inhibit bacterial urease, by measuring ^{13}C -labeled urea in blood and urine samples, following an intravenous load of ^{13}C -urea. Blood and urine ^{13}C -urea, plasma ammonia, plasma glutamine and blood urea will also be measured.

3. Background

It is well known that gut commensal bacteria modulate nutrient absorption, mucosal barrier fortification, xenobiotic metabolism, angiogenesis, and intestinal maturation. The gut microbiome also interacts strongly with the host in determining metabolic phenotypes. Microbial metabolism and co-metabolism has been described for various nutrients and metabolic products including vitamins, lipids, fatty acids, organic acids and amino acids. Gut microbial metabolism also affects urea cycle function more directly by contributing to portal ammonia via exogenous and endogenous pathways that include: 1) microbial breakdown of dietary protein and 2) the enzymatic hydrolysis of urea by urease to produce ammonia and carbonic acid. A number of gut dwelling bacteria produce urease including: *Proteus* species, *Helicobacter pylori*, and *Klebsiella*. Urea is transported from the blood to the intestinal lumen where it is hydrolyzed to ammonia by microbial urease. Studies in healthy human subjects indicate that up to 30% of liver-synthesized urea may enter the intestine where it can be hydrolyzed by microbial urease to produce ammonia. It is estimated that 15-30% of the nitrogen derived from microbial urea hydrolysis is incorporated back into urea by the liver. This process of recycling of urea is known as urea nitrogen salvage (UNS). UNS may be dependent on protein intake as well as microbial populations. For example, subjects, such as UCD patients, on a low protein diet showed greater UNS compared to controls. Secondary effects of gut bacteria are evident in urea cycle enzyme activity. Germ-free mice have significantly lower Ornithine Transcarbamylase (OTC) activity, and decreased urea cycle intermediates ornithine and arginine. In addition, liver slices from germ-free mice synthesize less urea compared to their conventional controls. Overall gut microbes contribute up to 50% or more of the portal blood ammonia pool.

Currently, the only approved clinical use of the drug for blockade of urease in bladder/renal proteus infections associated with renal struvite calculi (Lithostat, Mission Pharmacal, San Antonio, TX). The prescribing information indicates a recommended AHA dosing of 10-15 mg/kg/d (and 10 mg/kg/d in children), administered at 6-8 hour intervals when the stomach is empty. Children have tolerated a dose of 10 mg/kg/ satisfactorily for periods up to one year.

[figure not shown]
Enteral AHA has previously been administered to patients with hyperammonemia due to hepatic encephalopathy in two published reports^{6,7}. A single dose of oral 750 mg in adult patients was insufficient to result in any change in ammonia after 90 minutes in cirrhotic subjects free of *H. Pylori*⁷. However, in encephalopathy cirrhotic subjects administered AHA 20-60 mg/kg via naso-gastric tube, a statistically significant decreased in blood ammonia was observed⁶, with the effect most striking in subjects receiving a dose of 40-60 mg/kg/d.

This proposal would introduce a novel therapeutic approach for patients with UCD using a low-toxicity compound that may be particularly effective in patients with partial UCDs. There are two potential ways this approach may lower blood ammonia or excess nitrogen. The first is through blockage of new ammonia formation from urease. The second path may be increased consumption of residual dietary nitrogen by the gut flora in the absence of available nitrogen released through urease. Both effects may decrease the amount of nitrogen entering the portal vein. This new therapy will not interfere with other therapies, but would be complementary to them and may potentiate the nitrogen trapping effects of arginine and citrulline by preventing the degradation of the urea produced by their administration.

4. Study Design and Methods

This pilot crossover study will first evaluate the impact of AHA versus non-AHA primarily on ¹³CO₂ and secondarily on other biomarkers in healthy adults before applying the same crossover design to UCD subjects. A randomization table will determine if AHA or non-AHA will be performed first.

The figure below illustrates our study design:

Subjects will be required to fast for a minimum of 4 hours prior to beginning the study. Food consumption will not be permitted during the study; however subjects will be allowed to drink water or pedialyte throughout the study. Subjects will be observed and

various biomarkers will be collected throughout the 4-6 hours that they are studied. 5 mL of blood will be collected at each of the 7 time points shown above. Administration of [¹³C]-urea will be completed through an intravenous catheter. Blood draws will be done through the placement of a Heplock intravenous catheter on the opposite arm from where [¹³C]-urea was first administered. If there is not adequate vascular access, subjects will have a PICC (peripherally inserted central catheter) line placed instead.

Recruitment and enrollment: See Section 4.3, 8.4-5

Follow-up: Subjects will be followed throughout the duration of their participation.

Data collection: See Sections 5.9, 6, 7

